discharge. Because the attachment feature of SM was not available at the time of the pilot, we instead used a text-based format, embedded in the body of the SM (figure 1 in Appendix 2), for the pharmacist and Veteran to reconcile medications. As we will do in the proposed SMMRT Trial, we recruited hospitalized Veterans, registered them for MHV, and trained them to use MHV and SMMRT. After discharge, our pharmacist reviewed the CPRS records of 51 eligible Veterans and identified 108 clinically important medication discrepancies (median 2 per Veteran), mostly medications that the Veteran was taking but were omitted from the

discharge summary or discharge medication list. After correcting these discrepancies, the pharmacist sent SMMRT via SM to the Veteran. A total of 34 Veterans (67%) returned SMMRT. Of these 34 Veterans, 17 (50%) had additional discrepancies, most commonly duplicative medications prescribed for the Veteran at VA Boston and another VA facility. Nine of 10 Veterans completing post-intervention in-depth interviews (similar to those proposed in Aim 3) said they would use SMMRT again. Appendix 5 presents direct quotes about SMMRT from these Veteran participants. This study demonstrated the feasibility of recruiting hospitalized Veterans and training them in MHV and SM. Results highlighted the high prevalence of medication discrepancies immediately after discharge and the ability to detect and correct them by SMMRT.

#Aligning Medication Reconciliation and SM: A Qualitative Study of Providers' Perspectives.

In this study, published in *JMIR*,³⁹ we conducted in-depth interviews with 15 primary care providers to characterize ambulatory medication reconciliation, the use of SM in primary care, and perceptions of a SMMRT-like medication reconciliation system. Providers recognized the value of medication reconciliation, especially after hospital discharge, and suggested numerous challenges to medication reconciliation. Providers emphasized the importance of collaborating with pharmacists in reviewing Veterans' medication regimens.

#Qualitative Study of Pharmacists' Role in Medication Review and Reconciliation.

[name] recently completed a series of interviews with clinical pharmacists regarding their role in medication management. Preliminary analyses revealed considerable enthusiasm among pharmacists for developing relationships and monitoring patients to improve medication safety.

#Medication Discrepancies.

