The setting of Aim 1 will include not only the acute inpatient hospital (located on the West Roxbury Division Campus) but also the CLC, located on the Brockton Division Campus.

2. Recruitment and enrollment

Approximately ten (10) patients per week are discharged to home from the CLC each week. Because of the strong relationships developed between the clinical teams and the Veterans and their families during the long (compared with acute inpatient) hospitalizations, typically 3-4 weeks, Veterans are likely to be amenable to enrolling in a clinical research trial that they see their clinical team members advocating. Conservatively, we estimate that at least 2 patients each week will enroll in SMMRT, such that over the course of 12 months (50 weeks), a minimum of 100 patients would be enrolled. In addition, we have ensured that resources are available to enroll 140 patients at the West Roxbury setting, resulting in a total sample size of 240 subjects. Recruitment and enrollment processes will follow these steps:

1. Research staff will communicate regularly with clinical staff (nurses and clinicians) on the inpatient service at VA Boston's West Roxbury and Brockton Divisions
2. Research staff will identify any Veterans hospitalized on the Inpatient Service meeting the following criteria by reviewing CPRS, patient lists, and consulting with clinical staff:
 - a. age 18 years or older
 - b. having a VA primary care provider (PCP) at any VA facility in VISN-1
 - c. planned discharge home (as opposed to another facility)
 - d. anticipated to be discharged with at least 5 medications
3. Research staff will confirm with clinical staff that the Veteran/patient may be approached and informed about the study.
4. Research staff will approach the hospitalized Veteran to describe the study and seek informed consent for participation.
5. The research staff will briefly describe the study and then administer the Callahan cognition screener (see separate document) and the eligibility screening questions below.
6. If the Veteran passes the Callahan cognition screener and eligibility screening questions, the research staff member will seek to obtain informed consent and HIPAA Authorization.

Script for Aim 2 Eligibility Screening Questions (after Callahan Screening and before Informed Consent):

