- Thank you for allowing me the chance to tell you about our study. I would like to ask you a few questions first to see if you meet the requirements for eligibility. Would that be okay?

[figure not shown]
1. **Do you have access to a computer? Y/N** (*If yes, continue. If no skip to question 4*)
2. **Do you use a computer to connect to the internet, say to search websites or for email?**
3. ***If yes, Do you use secure messaging? If no, would you be willing to use it if required for this study?***
4. **Does anyone help you manage your medicines? Y/ N** (*If yes, continue. If no, not eligible, go to Verbal consent*)
5. **Does that person use a computer/ internet/ email? Y/N** (*If yes, continue. If no, not eligible, *Would you be willing to have your caregiver use secure messaging on your behalf if required for this study?**

If no to either 2 or 3: Unfortunately, you do not meet the criteria to participate in this study. Thank you for your time and interest.

→If Yes to 3 and 4, administer the Callahan screener. If patient passes the screener, then the patient is eligible. Continue on to ICF and HIPAA forms.

3. Randomization and intervention

Veterans successfully recruited and consented to participate will be randomly allocated to either UC or UC+SMMRT. Veterans randomized to UC+SMMRT will receive introduction to My HealtheVet and SMMRT. Within 3 business days of discharge, the SMMRT Research Pharmacist will engage with Veterans and/or their designated family members to conduct medication review and reconciliation via Secure Messaging. See randomization scheme below.

After baseline assessment is complete, participants will be randomly assigned via computer program to receive 1) usual care or 2) UC plus pharmacist-mediated medication reconciliation (SMMRT). After opening, the research assistant will inform the Veteran of the “treatment assignment.”

Overview of the Intervention

[figure not shown]
The intervention principally entails the creation of a personalized medication list for each Veteran/subject, incorporating most current data from Vista (the medical record) into a user-friendly PDF-file interface, i.e. the SMMRT. The research pharmacist will send the SMMRT via attachment to Secure Message to the Veteran and will then interact with the Veteran to ensure that the medical record accurately reflects what medications the Veteran is taking.

What Happens in the Intervention?

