We propose a two-arm RCT, with 120 participants in each arm. The main outcome measure will be combined number of medium- and high-significance medication discrepancies present at the 30-day follow-up. Conservative estimates suggest that we would expect a rate of 3.0 medium- or high-significance medication discrepancies per patient in the Usual Care group. Using a custom simulation, with two-tailed alpha error set at 5%, we calculated that this sample size (120 subjects per arm) would have 99.9% power to detect a lowering of the rate from 3.0 to 2.0 and 82% power to detect a lowering of the rate from 3.0 to 2.4.

6. Measures.

Study measures will be derived from baseline and 1-month follow-up interviews, as well as from CPRS.

Predictor Variable. The predictor variable will be the experimental condition (i.e., Usual Care SMMRT), assigned by random allocation (see above).

Main Outcome Variable. The primary outcome measure will be medication discrepancies detected 30 days after discharge. Secondary outcome measures will be 30-day hospital utilization (combined readmissions plus emergency department use) and Veterans' self-efficacy in medication use.

Secondary Outcome Variables. Secondary endpoints, ascertained through a combination of CPRS review

plus follow-up interview with participants, include community tenure (days spent outside of the hospital), medication discrepancies (overall and by subtype, i.e., omissions, commissions, duplications, and alterations in dose or frequency); health status (SF-12 health status scale; 12 items, 2-3 minutes), medication use self-efficacy (score of 0 to 8, based on validated 8-item yes/no MUSE scale;⁶² 3 minutes); and the Care Transition Measure (score of 0 to 100, based on validated 15-item, 4-point [strongly agree, agree, disagree, strongly disagree] scale, linear transformed to 0 to 100 scale,⁶³ 5 minutes).

Other Variables. Prior to randomization, we will stratify participants on the basis of My HealtheVet in-person authentication status (yes/no) and VA Boston primary care (yes/no); see above Figure 2 and Section 4.e.5. Baseline data will include age, educational level, race/ethnicity. At baseline, we will administer the 7-item REALM-SF health literacy scale,⁶⁴ the SF-12, and the medication use self-efficacy scale (MUSE). During the 30-day follow-up we will re-administer the SF-12, the CARE Transition measure and the MUSE.

7. Statistical Analysis.

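### Enrolment setting (acute hospital or CLC) is neither a named stratum nor a covariate in the primary analysis, which costs precision if discrepancy rates differ by setting

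*Combined protocol and SAP*

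**What the plan says.** Section 1 (Study setting and population) of the Aim 1 methods takes in "not only the acute inpatient hospital (located on the West Roxbury Division Campus) but also the CLC, located on the Brockton Division Campus". Section 2 (Recruitment and enrollment) builds the sample from two sources. For the CLC, "over the course of 12 months (50 weeks), a minimum of 100 patients would be enrolled"; in addition, "resources are available to enroll 140 patients at the West Roxbury setting, resulting in a total sample size of 240 subjects". The only contrast drawn between the settings is that CLC staff and Veterans form relationships "during the long (compared with acute inpatient) hospitalizations, typically 3-4 weeks". Eligibility is the same in both: for example, a primary care provider at any VISN-1 facility, and "anticipated to be discharged with at least 5 medications". The hypothesis in (1)(b) names discharge from the hospital and from the skilled nursing facility.

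Section 3 (Randomization and intervention) says that "participants will be randomly assigned via computer program" and refers to a scheme. Section 6 (Measures, Other Variables) gives the strata: "we will stratify participants on the basis of My HealtheVet in-person authentication status (yes/no) and VA Boston primary care (yes/no". Setting appears neither there nor among the baseline data listed next.

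Section 7 (Statistical Analysis, Preliminary Analyses) checks balance on socio-demographic variables and leaves potential confounders out of the primary analysis. Sensitivity analyses adjust for plausible confounders that show a large imbalance.

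**The concern.** Setting is known for every Veteran before randomisation and may well be prognostic. CLC stays are much longer. In the pilot, most discrepancies found on record review were medicines that the Veteran took but that were missing from the discharge summary or discharge list. It is an inference, but a reasonable one, that such omissions vary with the discharging unit. The pilot cannot settle the matter: "we recruited hospitalized Veterans, registered them for MHV, and trained them to use MHV and SMMRT", and it reports no figures by setting. VA Boston primary care is not a stated stand-in for setting, since a Veteran on either campus may have a provider anywhere in VISN-1.

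If discrepancy counts do differ by setting, the arms can receive different CLC shares by chance, and nothing in the primary analysis corrects for it. The planned sensitivity adjustment is triggered by what is seen, does not name setting, and leaves the primary estimate as it was. The plan claims 82% power at the smaller effect, so there is little room to lose precision.

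**Working it through.** **Inputs from the documents.** 120 per arm; two-sided alpha 5%; Usual Care rate 3.0; alternatives 2.0 and 2.4, with stated power of 99.9% and 82% (section 5); 100 CLC and 140 acute Veterans (section 2).

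**Assumption.** D, the difference in mean discrepancies between settings, is not in the documents. The range used is 0 to 2, with the overall Usual Care mean held at 3.0.

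**1. The plan's own power.** For Poisson counts, SE = sqrt((r0 + r1)/n).
- 3.0 vs 2.0: SE = sqrt(5.0/120) = 0.204; 1.0/0.204 − 1.96 = 2.94; power 99.8%.
- 3.0 vs 2.4: SE = sqrt(5.4/120) = 0.212; 0.6/0.212 − 1.96 = 0.87; power 80.7%. A Poisson simulation gives 81.0%.

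Both are within 2 points of the stated figures. This calculation has pure Poisson variation and so no difference between settings.

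**2. Chance imbalance.** Allocate 100 CLC Veterans over two arms of 120 without regard to setting. The number in one arm is hypergeometric, with mean 50 and SD = sqrt(120 × (100/240) × (140/240) × (120/239)) = 3.83. The difference in CLC share has SD 2 × 3.83/120 = 6.4 points. It is at least 10 points in 15.0% of trials, at least 15 points in 2.6% and at least 20 points in 0.3%.

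**3. Power without adjustment.** A gap D adds (100/240) × (140/240) × D² = 0.243 D² to the variance in each arm, so SE = sqrt((5.4 + 2 × 0.243 D²)/120). Example at D = 1: sqrt(5.886/120) = 0.221; 0.6/0.221 − 1.96 = 0.75; power 77.3%. The shift column is 1.96 × 0.0638 × D, the movement in the arm difference at a 1.96 SD imbalance. The last column is power given that imbalance, against or in favour of SMMRT.

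| D | Power, 3.0 vs 2.4 | Shift (share of 0.6) | Conditional power |
|---|---|---|---|
| 0 | 80.7% | 0 | – |
| 0.5 | 79.9% | 0.06 (10%) | 70.9% to 87.3% |
| 1 | 77.3% | 0.13 (21%) | 57.6% to 91.5% |
| 2 | 67.9% | 0.25 (42%) | 26.2% to 95.7% |

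The shift and the larger SE are one effect. The variance of the shift is 0.0638² × D² = 0.0041 D², and the variance added to the SE is 2 × 0.243 D²/120 = 0.0041 D².

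**4. What restores power.** Simulation with 20,000 runs per cell and a proportional effect of 2.4/3.0 = 0.8:

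| D | Neither | Stratify only | Adjust only | Both |
|---|---|---|---|---|
| 0.5 | 80.1% | 80.7% | 80.5% | 81.2% |
| 1 | 77.8% | 78.6% | 80.6% | 80.7% |
| 2 | 70.6% | 72.8% | 81.0% | 81.1% |

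With no treatment effect, rejection with neither step is 5.0%, 4.9% and 5.0% for the three gaps. Stratifying with an unadjusted test gives 4.8%, 4.4% and 2.2%, so that test becomes conservative. Adjustment does most of the work.

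**The case against.** The strongest objection is that the decisive input is missing. The documents contrast the settings only by length of stay, apply the same eligibility to both and give no discrepancy rate for either. At a gap of 0.5 the loss is under one point of power. A gap of 2 needs setting means of about 4.2 and 2.2. A typical imbalance is about 5 points, which at a gap of 1 moves the estimate by 0.05, or 8% of 0.6. A 1.96 SD imbalance would move it by the full 0.6 only at a gap of about 4.8. All of this stands, and it limits the point to a modest one.

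It is also fair that the sensitivity analyses could pick up setting. They would do so only after a large imbalance had been seen and judged, and the primary estimate would not change.

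The randomisation scheme cited in section 3 may be in a figure that is not reproduced in the text available. The section number cited beside the strata does not occur in this document. A setting stratum therefore cannot be ruled out. It would not remove the point, because a stratum without the covariate recovers little.

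A reader might infer that the SMMRT effect is confounded with setting, or that false positives are inflated. The documents do not support this: allocation is random, and the ordinary standard error already carries this variation. Nor do they support reading the settings as very different populations, or 100 and 140 as fixed quotas. The first is an expected minimum and the second is resourced capacity.

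**Conclusion.** The point holds as a cheap gain in precision. On the visible text, setting is protected neither in the allocation nor in the primary analysis, although the hypothesis spans both settings. The consequence is lost precision, and conditional bias when the CLC shares happen to differ. It is not a threat to validity.

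Against about 81% with no gap, power for 3.0 vs 2.4 is about 80% at a gap of 0.5, 77% at 1 and 68% at 2. The loss is trivial at the low end and material only if the settings differ by well over one discrepancy per Veteran. The gap is assumed throughout.

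The figures use the count outcome behind the power statement. Section 7 names logistic regression, so the percentages may not carry over to that model. The absence of setting from the primary analysis is the same under either model.

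**What to change.** Before outcome data are reviewed, amend section 7 so that the primary model includes study arm and enrolment setting (West Roxbury acute or Brockton CLC) as a prespecified covariate, whatever imbalance is observed. Add setting to the baseline data in section 6, and report the treatment effect by setting descriptively. If the primary model remains logistic, state whether the reported odds ratio is conditional on setting or marginal, because the two differ even without imbalance. The cost is one recorded field and a few lines of text, with no extra Veterans.

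As a secondary step, add setting to the computer allocation if enrolment has not begun and the randomisation figure does not already include it. The downside is more and smaller strata: 2 × 2 × 2 = 8, averaging 240/8 = 30 Veterans, with some possibly much smaller. The two existing factors should stay, since nothing in the documents marks either as dispensable. If enrolment has begun, the covariate alone is enough.

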Preliminary Analyses. In preliminary analyses, descriptive statistics and bivariate associations will be computed. Then we will assess whether there are differences between the study arms for socio-demographic variables. We will assess imbalance formally using Analysis of Variance for continuous variables and Chi Square tests for dichotomous variables. In order to confound any observed effect of the treatment, a covariate must be imbalanced between the arms and also associated with the outcome. Thus, we will judge how plausible confounding is based on the formal tests, the degree of imbalance, and the plausibility of association with the outcome. Primary analysis will not include any potential confounders, but sensitivity analyses will adjust for plausible confounding variables with large imbalance between the arms.

Statistical Analyses. The primary hypothesis is that SMMRT will result in a reduction in 30-day medication discrepancies as compared with UC. The main outcome will be tested by a two-step analysis. First, we will conduct a logistic regression to compare SMMRT vs. UC. We will take an intent-to-treat approach to the analysis; Veterans will be included in our primary analyses regardless of their level of adherence with their assigned intervention. For participants who do not complete the telephone assessment, we will rely on CPRS/CDW data for outcome assessment.

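### No pre-randomisation medication count is planned as baseline data or covariate, although it plausibly predicts the primary discrepancy count; the precision gain depends on assumptions and needs a count model

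*Combined protocol and SAP*

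**What the plan says.** Section 5 (Sample size and power) makes the main outcome the "combined number of medium- and high-significance medication discrepancies present at the 30-day follow-up". It powers the trial on rates: "we would expect a rate of 3.0 medium- or high-significance medication discrepancies per patient in the Usual Care group", with 82% power for a fall to 2.4 and "99.9% power to detect a lowering of the rate from 3.0 to 2.0".

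Section 6 (Measures, Other Variables) states: "Baseline data will include age, educational level, race/ethnicity". It adds REALM-SF, SF-12 and MUSE at baseline, and stratifies on portal authentication status and on whether primary care is at VA Boston. A medication count appears in neither list.

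Section 2 (Recruitment and enrollment) requires that a Veteran be "anticipated to be discharged with at least 5 medications". Staff judge this from CPRS, patient lists and conversation with clinical staff. Nothing says that a number is recorded.

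Section 7 (Statistical Analysis) directs the between-arm imbalance check at socio-demographic variables and then states: "Primary analysis will not include any potential confounders". Adjustment is left to sensitivity analyses, for plausible confounders with large imbalance. The main outcome is to be tested in two steps. The first is a logistic regression and the second is not described.

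**The concern.** Discrepancies are found by comparing the list of drugs a Veteran reports taking with the list in the record (section 4, Ascertainment of Outcome). Longer lists give more opportunities for a mismatch, so a Veteran on 5 drugs and one on 20 probably have different expected counts. If so, medication number adds between-patient variance that an unadjusted comparison carries as noise. A pre-specified covariate could remove some of it.

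A chance imbalance in medication number would also fall outside the planned check. It would not bias the randomised test, since its expected size is already part of the standard error, but it would make one realised result harder to interpret.

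A count taken at 30 days cannot stand in. In the SMMRT arm only, the pharmacist begins reviewing and correcting the record within 3 business days of discharge, so a later count can itself be affected by treatment.

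**Working it through.** **Inputs.** From section 5: 120 per arm, two-sided 5%, control rate 3.0, alternative 2.4. The documents give neither the spread of medication counts nor their link to discrepancies. Assumed here: mean 10 medications with SD 2, 3 or 4 (CV 0.2, 0.3 or 0.4), rate proportional to count, and residual overdispersion k of 0, 0.2 or 0.5.

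**Step 1: reproduce the stated power.** With a pure Poisson count, the SE of the log rate ratio is sqrt(1/(120×3.0) + 1/(120×2.4)) = sqrt(0.00625) = 0.0791. Then ln(3.0/2.4)/0.0791 = 0.2231/0.0791 = 2.82, and Φ(2.82 − 1.96) = 80.6%. A test on the difference gives 0.6/sqrt(5.4/120) = 2.83, or 80.7%. For 3.0 to 2.0 the power is 99.8%. The plan states 82% and 99.9%, so its figures agree with a model in which every Veteran in an arm has the same rate.

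**Step 2: let medication number vary.** Unadjusted overdispersion is T = (1 + CV²)(1 + k) − 1. Adjusting for log count leaves k. The SE is sqrt((1/3.0 + 1/2.4 + 2T)/120) unadjusted, with k in place of T when adjusted. Example with CV 0.3 and k 0: T = 0.09, SE = sqrt(0.93/120) = 0.0880, and Φ(0.2231/0.0880 − 1.96) = 71.7%. Adjusted, it returns to 80.6%. The variance ratio is 0.93/0.75 = 1.24.

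| CV | k | Unadjusted | Adjusted | Gain (points) | Variance ratio |
|---|---|---|---|---|---|
| 0.2 | 0 | 76.5% | 80.6% | 4.1 | 1.11 |
| 0.3 | 0 | 71.7% | 80.6% | 8.9 | 1.24 |
| 0.4 | 0 | 65.7% | 80.6% | 14.9 | 1.43 |
| 0.2 | 0.2 | 59.1% | 62.5% | 3.4 | 1.08 |
| 0.3 | 0.2 | 55.2% | 62.5% | 7.3 | 1.19 |
| 0.4 | 0.2 | 50.5% | 62.5% | 12.0 | 1.33 |
| 0.2 | 0.5 | 43.2% | 45.5% | 2.3 | 1.07 |
| 0.3 | 0.5 | 40.5% | 45.5% | 5.0 | 1.15 |
| 0.4 | 0.5 | 37.3% | 45.5% | 8.2 | 1.27 |

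The variance ratios correspond to about 7% to 43% more patients.

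**Step 3: check by simulation.** Each setting used 1,500 trials, with medications equal to 5 plus a rounded gamma of mean 5, analysed by Poisson regression with robust SE. Monte Carlo error is about sqrt(0.8×0.2/1500) = 1 point.

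- Proportional, no other heterogeneity: 73.3% to 81.9% (SD 3); 65.1% to 81.9% (SD 4).
- Proportional, k 0.3: 50.7% to 55.3% (SD 3); 45.7% to 52.6% (SD 4).
- Rate proportional to the square root of the count: 80.5% to 82.3% (SD 3, k 0); 53.6% to 54.7% (SD 4, k 0.3).
- No link: 56.1% to 56.0% (SD 4, k 0.3).

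With residual overdispersion the formula is somewhat optimistic. At CV 0.4 and k 0.3 it gives T = 0.508, and power of 45.2% to 55.7%: a gain of 10.5 points, against 6.9 simulated. The 12-point entry in the table is best read as an upper end.

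**Step 4: the logistic step.** Assume the outcome is cut at any versus none. The proportions are 1 − e^−3.0 = 0.950 and 1 − e^−2.4 = 0.909, and power is about 24%. In simulation, adding log count changes it from 21.2% to 21.1% (SD 3, k 0) and from 15.3% to 16.4% (SD 4, k 0.3). The first setting's SE rises slightly, from 0.476 to 0.487.

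**Step 5: chance imbalance.** Under proportionality, a 1.96-SD difference in mean count between arms is 1.96 × CV × sqrt(2/120). That is 7.6% at CV 0.3 and 10.1% at CV 0.4, against a 20% target reduction.

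**The case against.** An unadjusted analysis of a randomised trial is valid, and section 7 chooses it openly. That stands: this is a matter of efficiency, not an error.

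A reader might infer four stronger things that the documents do not support.

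- **That the medication count bounds the outcome.** The pilot (section (3), Work Accomplished) found mostly drugs the Veteran was taking that were missing from the discharge summary or list. Such drugs need not be in a CPRS count, so strict proportionality is doubtful and only a tendency to scale together is defensible.
- **That precision is there for free once the number is written down.** Section 7 bars covariates from the primary analysis and names logistic regression. Under an any-versus-none cut the covariate does essentially nothing, and the mismatch between count outcome and logistic model costs far more power than the missing covariate.
- **That staff already hold the count.** Screening applies an anticipated threshold, and an inpatient's active list need not match the discharge regimen.
- **That an imbalance could never be seen or handled.** The baseline list is not worded as closed, measures also come from CPRS, and sensitivity adjustment is allowed. A count could be abstracted later, but choosing it then would be an unplanned decision.

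None of this supplies the variable. No section plans a pre-randomisation count or a rule for using it.

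**Conclusion.** The point holds as an inexpensive improvement. A plausible predictor of the primary count is absent from the planned baseline data, strata, imbalance check and primary model.

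The gain at 3.0 versus 2.4 is about 4 to 15 power points under proportionality with SD 2 to 4 around a mean of 10 and no other heterogeneity. A square-root link cuts it to about 1 to 2 points in the settings run. With residual overdispersion it is mostly 8 points or fewer, with 12 the most favourable formula result, and the stated 82% is then not restored. It is zero with no link.

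All of these figures rest on assumed spreads and links, and all require a count model.

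**What to change.** 1. **Collect.** Before randomisation, abstract from CPRS the number of active medications for every Veteran in both arms, under one written definition and time point. Never use a count taken after the pharmacist begins editing the record. Tie the field to screening or consent rather than to the baseline interview: section 3 places randomisation after the baseline assessment, while section (5), Human Subjects, places the interview after randomisation.
2. **List and report.** Add it to the baseline data in section 6 and tabulate it by arm.
3. **Model.** Amend section 7 so that log medication count is a pre-specified covariate whatever imbalance is observed, in a negative binomial model or Poisson with robust SE. Either matches the rate-based outcome and power statement in section 5. Keep the unadjusted estimate as a supporting analysis.

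The cost is one abstracted field that needs a definition, one model term, and a departure from the stated unadjusted primary analysis. There is no added visit or burden for Veterans.

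### The only covariate-adjusted analysis takes its covariates from observed baseline imbalance between randomised arms, which limits its precision and its value as a robustness check

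*Combined protocol and SAP*

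**What the plan says.** The rule is in the combined protocol and SAP, section (4) Work Proposed, Methods for Aim 1, item 7 (Statistical Analysis), under Preliminary Analyses. After descriptive statistics and bivariate associations, the arms are compared on socio-demographic variables: "We will assess imbalance formally using Analysis of Variance for continuous variables and Chi Square tests for dichotomous variables". The plan reasons that a covariate can confound only if it both differs between arms and is related to the outcome. So "we will judge how plausible confounding is based on the formal tests", along with the size of the imbalance and the credibility of a link with the outcome. The primary analysis carries none of these covariates, but "sensitivity analyses will adjust for plausible confounding variables with large imbalance between the arms".

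The plan gives no significance level for the tests, no definition of a large imbalance and no list of candidate covariates.

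No other stated analysis has covariates in its outcome model. The primary model is a logistic regression comparing the two arms. The inverse-probability-weighted analysis for drop-out has study arm as its only stated predictor.

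Item 6 (Measures, Other Variables) stratifies on My HealtheVet in-person authentication and VA Boston primary care. It also lists the baseline data: age, education, race/ethnicity, REALM-SF, SF-12 and MUSE. The stratification factors appear in no stated outcome model.

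**The concern.** In a randomised trial the null hypothesis of a baseline comparison is true by design. A small p-value shows that the allocation came out unusually. It does not show that the covariate matters for the outcome.

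A covariate moves the unadjusted estimate by the product of its imbalance and its association with the outcome. The plan makes large imbalance a condition of entry, and weighs association only among variables that meet it. Three things follow:

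- A strong predictor with moderate imbalance is left out, although it may move the estimate appreciably.
- The covariate set is unknown until the arms have been compared, and it then rests on undefined judgement.
- If nothing looks imbalanced, the plan triggers no adjusted analysis.

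At stake is the usefulness of the sensitivity analysis. A reader wants it to show whether the primary result survives adjustment for what predicts discrepancies. Under this rule its content depends on chance.

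**Working it through.** **1. The plan's own figure.** The inputs come from item 5 (Sample size and power): "We propose a two-arm RCT, with 120 participants in each arm"; two-sided alpha of 5%; "we would expect a rate of 3.0 medium- or high-significance medication discrepancies per patient in the Usual Care group"; alternatives of 2.0 and 2.4. The method is given only as "Using a custom simulation". I assume Poisson counts, no covariates and no drop-out. Power = Φ(difference / √((λ0+λ1)/120) − 1.96).

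- 3.0 vs 2.0: 1.0/√(5.0/120) = 4.899, so power is Φ(2.939) = 99.8% (plan: 99.9%).
- 3.0 vs 2.4: 0.6/√(5.4/120) = 2.828, so power is Φ(0.868) = 80.7% (plan: 82%).

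Both agree within two points, so the sample size does not rely on adjustment.

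**2. Share of the variance reduction that the rule keeps.** Let z be the standardised baseline imbalance (standard normal under randomisation) and r the covariate-outcome correlation. The unadjusted estimate carries a chance component of r·z standard errors, and adjustment removes it. Always adjusting removes variance r²·E[z²] = r². Adjusting only when |z|>c removes r²·E[z²; |z|>c]. The share kept is therefore P(|z|>c) + 2c·φ(c), whatever r is. The thresholds below are assumptions, because the plan states none. A standardised mean difference (SMD) converts as z = SMD·√(120/2) = 7.746·SMD.

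| Assumed trigger | c | P(\|z\|>c) | 2c·φ(c) | Share kept |
|---|---|---|---|---|
| p<0.05 | 1.960 | 0.050 | 0.229 | 28% |
| p<0.10 | 1.645 | 0.100 | 0.339 | 44% |
| \|SMD\|>0.2 | 1.549 | 0.121 | 0.372 | 49% |

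**3. What the rule can leave out.** Take a covariate with z = 1.5 (p = 0.13; SMD = 1.5/7.746 = 0.19). With a Poisson standard error of √(6/120) = 0.224 discrepancies, it shifts the unadjusted estimate by:

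- r = 0.4: 0.60 SE, or 0.13 discrepancies (22% of the planned 0.6)
- r = 0.2: 0.30 SE, or 0.07 discrepancies
- r = 0.1: 0.15 SE, or 0.03 discrepancies

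The documents give no value for r.

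**4. Whether any adjusted analysis is run.** If the trigger were p<0.05 and covariates were independent, the chance that at least one is flagged is 1 − 0.95³ = 14% for three covariates and 1 − 0.95⁷ = 30% for seven. So in 86% or 70% of trials none would be flagged.

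**5. Absolute gain.** For 3.0 vs 2.4, one pre-specified covariate explaining a share R² of outcome variance divides 2.828 by √(1−R²). The triggered column is from 200,000 simulated trials with a p<0.05 trigger.

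| R² (assumed) | Always adjust | Adjust if p<0.05 | Unadjusted N with equal precision, 240/(1−R²) |
|---|---|---|---|
| 0.1 | 84.6% | 81.3% | 267 |
| 0.2 | 88.5% | 81.7% | 300 |
| 0.3 | 92.3% | 82.2% | 343 |

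These are powers of an adjusted analysis of the count, against 80.7% unadjusted. They are not powers of the planned primary test. That test is logistic, and the plan does not say how the count is dichotomised. A check of 3,000 simulated trials with R² about 0.28 gave, for unadjusted, always adjusted and triggered (p<0.05):

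- logistic, three or more discrepancies: 48.0%, 55.6%, 48.0%
- logistic, one or more discrepancies: 20.3%, 20.8%, 20.0%

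At the second cut-off there is almost no gain to lose.

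**The case against.** The strongest reply is that little depends on this rule. The primary test is fixed in advance as unadjusted, it is a valid randomised comparison, and the power figures reproduce without covariates. The rule governs only sensitivity analyses, which are not there to carry power. The plan also does not select on p-values alone: it names three criteria and no significance level, so the p<0.05 trigger is the reviewer's assumption. An analyst weighing the size of the imbalance could well include a covariate with a standardised difference of 0.25. The correlations have no source in the documents, and with a logistic cut-off of one or more discrepancies the gain nearly vanishes.

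All of this stands, and it limits the size of the point. It does not rescue the rule, because credibility of association still counts only among variables already judged imbalanced, and nothing is named beforehand.

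A reader might make two stronger inferences that the documents do not support:

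- **Inflated type I error.** Given z = 1.5 and r = 0.4, an unadjusted test has a conditional type I error of about 7%; at z = 1.9 and r = 0.5, about 12%. These figures belong to any unadjusted test given a chance imbalance, and the selection rule does not produce them. Over all randomisations the unadjusted test holds its level. If the triggered analysis were itself used as the test, it would be slightly conservative in simulation (4.5% at R² = 0.2, 4.0% at R² = 0.4).
- **Covariates chosen with knowledge of which arm is which.** The documents neither state nor exclude coded arm labels, and comparing baseline variables does not require outcome data. What the text does establish is that selection follows the comparison of the arms.

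**Conclusion.** The point holds, confined to the adjusted sensitivity analysis. Large imbalance is a stated condition of entry, so the covariate set depends on chance and on undefined judgement, and it may be empty. The unadjusted primary test and its type I error are not affected.

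Under normal theory, imbalance-triggered adjustment keeps between 28% (p<0.05) and 49% (|SMD|>0.2) of the variance reduction from always adjusting, so at each assumed threshold at least about half is lost. The share does not depend on the correlation, but it does depend on the threshold. The absolute loss cannot be fixed from the documents, since it needs the covariate-outcome correlations and the logistic cut-off. It may be material at a cut-off of three or more discrepancies and near zero at one or more. The selection fault remains in either case. The change is worth making because it costs so little, but the trial's main conclusion does not hang on it.

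**What to change.** In item 7, Preliminary Analyses:

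- Drop the ANOVA and chi-square tests as a way of choosing covariates, and describe baseline balance by arm without p-values.
- Before any comparison of the arms, name the covariates of the adjusted sensitivity analysis: the two stratification factors (My HealtheVet authentication and VA Boston primary care) plus a short list of baseline variables already collected and expected to predict discrepancies, for example age, education and REALM-SF.
- State that this analysis will be run and reported with those covariates whatever imbalance is observed.

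The cost is SAP wording only. No new data or change in sample size is needed, and the primary analysis can stay unadjusted as planned. The primary test gains no power from this change; what improves is the sensitivity analysis.
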